## 2 ELIGIBILITY ASSESSMENT AND ENROLLMENT

### 2.1 Eligibility Criteria

#### 2.1.1 Inclusion Criteria

2.1.1.1 Subject is  $\geq 18$  years old.

2.1.1.2 Subjects with clinically localized prostate cancer (outside pathology is acceptable) must have image guided biopsy confirmed prostate cancer and sufficient tissue available (obtained before or after 20 weeks of Eovist® injection) for OATP1B3 expression.

2.1.1.3 Subjects with advanced disease who have failed hormone therapy and who have sufficient tissue (obtained before or after 20 weeks of Eovist® injection) from a soft tissue or metastatic bone lesion (measuring  $\geq 1.5$ cm in diameter at CT or MRI scan) available for OATP1B3 expression.

or

2.1.1.4 Subjects, for whom tissue is not available, must have a soft tissue or metastatic bone lesion that can be biopsied and be willing to undergo percutaneous biopsy to obtain tissue for OATP1B3 expression.

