#### **3.9.1 Criteria for Removal from Protocol**

- Investigators have the right to withdraw subjects from the study in the event of illness, AEs, or other reasons concerning the health or well-being of the subject, or in the case of lack of co-operation.
- Subject completes Eovist® enhanced MRI and has biopsy of the target lesion
- Patient requests to be taken off study
- Patient non-compliance with protocol guidelines

- Unacceptable treatment related toxicity as described in section **10.2.2**

Patient may not be taken off study until unacceptable toxicities have stabilized or resolved.

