#### **7.3.2 Secondary Efficacy Analysis**

The secondary objective of the study is to evaluate Eovist® MR parameters with respect to OATP1B3 lesion expression.

Imaging will be performed on 2 subgroups of prostate cancer patients. Subgroup 1 consists of early stage (non-metastatic) patients, subgroup 2 late stage (confirmed metastatic with prior hormonal ablation therapy) patients. It is expected that OATP1B3 expression is higher in late stage patients (subgroup 2) than in early stage patients.

For patients in subgroup 2, expression of OATP1B3 will be determined in soft tissue or bone lesions taken from biopsy and will be correlated with MRI signal change by both Pearson and Spearman correlation coefficient.

As OATP1B3 SNPs also alter androgen uptake, affecting outcome of androgen deprivation therapy (ADT) [3, 4], genotype will also be compared to progression-free survival on ADT. Genotypes will be compared to these endpoints using the chi-squared and/or Fisher's exact test, or the log-rank test as appropriate.

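### Section 7.3.2 plans a formal test of genotype against progression-free survival on ADT that this design cannot support, because advanced-disease men admitted under 2.1.1.3 have already failed hormone therapy

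*Combined protocol and SAP*

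**What the plan says.** In 7.3.2, after the correlation of OATP1B3 expression with MRI signal, the plan adds that "genotype will also be compared to progression-free survival on ADT". The method is "using the chi-squared and/or Fisher's exact test, or the log-rank test as appropriate". The section does not say which subgroup enters, when the clock starts, what counts as progression, or how selection at entry is handled.

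Eligibility (2.1.1) sets who can contribute:

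- **Arm 2, main route (2.1.1.3):** "Subjects with advanced disease who have failed hormone therapy and who have sufficient tissue".
- **Arm 2, alternative route (2.1.1.4):** "Subjects, for whom tissue is not available, must have a soft tissue or metastatic bone lesion that can be biopsied". This item does not repeat the hormone-failure condition. Section 7.3.2 itself describes "subgroup 2 late stage (confirmed metastatic with prior hormonal ablation therapy) patients", which requires earlier treatment and does not mention failure.
- **Arm 1 (2.1.1.2):** "Subjects with clinically localized prostate cancer (outside pathology is acceptable) must have image guided biopsy confirmed prostate cancer". Nothing here requires ADT.

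Section 3.9 takes subjects off study when procedures are done, and 3.9.1 lists among the removal criteria "Subject completes Eovist® enhanced MRI and has biopsy of the target lesion". The calendar in 3.6 has no visit for assessing progression. None of the objectives in 1.1 mentions genotype or progression-free survival.

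**The concern.** A time-to-progression comparison needs people who start at risk and are followed until they progress or are censored. Here, men entering under 2.1.1.3 are included because the event has happened. Men still responding to ADT at the time of recruitment cannot enter by that route. Any data on time on ADT must be retrospective, and the planned tests take no account of how the men were sampled.

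The stake is a p-value, listed under secondary efficacy, that cannot be interpreted. A null result could reflect selection or lack of power. A positive one would rest on a very small, selected group. Section 1.2.3 cites an earlier study of the same question in 68 men treated with ADT. That cohort is not described as restricted to ADT failures, so the two results would not be comparable.

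**Working it through.** The plan gives no effect size, event count or power for this comparison. The figures in 7.4 concern the paired signal change, so there is nothing to reproduce here.

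**1. Binary test.** Among n men admitted under 2.1.1.3, all n have failed hormone therapy. If failure is the progression event, a genotype by progressed/not-progressed table has an empty column, and chi-squared and Fisher have nothing to test.

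**2. Log-rank test: illustration of right truncation.** These assumptions are not in the documents: exponential time T on ADT; median 30 months in the slower genotype; true hazard ratio 1.5; equal genotype groups; ADT start uniform over the W months before enrolment. A man can be sampled only if T is shorter than the time since he started ADT.

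- Rates: λ₀ = ln 2/30 = 0.0231 and λ₁ = 1.5 × 0.0231 = 0.0347 per month.
- Probability of being sampled: 1 − (1 − e^(−λW))/(λW). For W = 60 this is 1 − 0.75/1.386 = 0.459 and 1 − 0.875/2.079 = 0.579, on average 52%.
- Mean T among those sampled: [1/λ − 2/(λ²W) + e^(−λW)(1/λ + 2/(λ²W))] divided by that probability.
- Slower genotype, W = 60: (43.28 − 62.44 + 0.25 × 105.72)/0.459 = 15.8 months.
- Faster genotype, W = 60: (28.85 − 27.75 + 0.125 × 56.60)/0.579 = 14.1 months.
- Ratio of means, which equals the crude event-rate ratio because all sampled men have events: 15.84/14.12 = 1.12. Without truncation it is 43.28/28.85 = 1.5.

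A log-rank test compares hazards, so the Cox hazard ratio from large simulated samples is also shown (repeat runs differ by about 0.01):

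| Look-back W (months) | Crude ratio | Cox hazard ratio |
|---|---|---|
| 36 | 1.07 | 1.08 |
| 60 | 1.12 | 1.15 |
| 120 | 1.23 | 1.26 |
| 360 | 1.42 | 1.42 |

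**3. Sensitivity of size and direction.** A second simulation used a true hazard ratio of 1.76, assumed medians of 1.5 to 3 years on ADT, a median of 2 years' survival after failure, and half the men carriers. The 1.76 is borrowed from the prostate-cancer mortality result in 1.2.3 and is not an estimate for time on ADT. The apparent ratio was 1.21 to 1.38 with a 5-year window, 1.41 to 1.63 with 10 years, and 1.75 with 30 years. When survival after failure was made proportional to time on ADT, the 30-year figure became 2.21, away from the null. Men with long times on ADT are then over-represented among those alive to enrol.

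**4. Power, setting selection aside.** Log-rank power ≈ Φ(√(d·p·(1 − p)) × ln HR − 1.96), with d events, carrier share p and two-sided 5% assumed. The plan gives 15 advanced-disease subjects (Precis, 7.1) or 10 (3.1), so both are used.

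- HR 1.76 (ln = 0.565), d = 15, p = 0.5: Φ(1.936 × 0.565 − 1.96) = 19%. With p = 0.2: 14%.
- HR 1.76, d = 10: 14% and 11%.
- HR 1.5 (ln = 0.405), p = 0.5: 12% with d = 15 and 9% with d = 10.
- Events for 80% power at HR 1.76, p = 0.5: 4 × (1.96 + 0.842)²/0.565² ≈ 99.

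As a cross-check, treat the cited P = 0.048 in 68 men as the true effect: z = 1.977, and 1.977 × √(15/68) = 0.929, which gives about 15% power. For 10 men it is about 12%. If only 50 to 80% of the 68 had events (not stated), scaling by events to 15 gives about 26% down to 18%.

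**The case against.** A reader might infer that the comparison is simply biased toward no difference. The documents do not support that as a certainty. Section 1.2.1 says progression on ADT is nearly universal in time, so a sample of failures need not be a sample of fast failures. With a long look-back the attenuation largely fades, and under one plausible survival pattern it reverses. The plan gives no ADT start times, so neither size nor direction can be settled. This part of the objection stands.

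Three narrower points also stand:

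- Arm 1 does not add bias toward the null. Men never given ADT have no value for this endpoint, and 7.3.2 does not say they enter the comparison.
- It is too strong to say that every arm 2 subject must have failed hormone therapy, because 2.1.1.4 does not repeat that condition.
- It is too strong to say that the data cannot exist. Section 3.6.1.1 collects medical and medication history, and 6.4.1 keeps samples linked to diagnosis and death dates for genotype work. The gap is that ADT start and failure dates are not named.

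It is also fair that this is one side analysis in a pilot study, with no power claim. None of this rescues the tests, however. The binary test remains degenerate under 2.1.1.3, the log-rank test still ignores selection on the event, and the sample remains very small.

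**Conclusion.** The concern holds as a defect in a stated analysis: the genotype comparison is not interpretable as planned. That men admitted under 2.1.1.3 are selected on the event, and that no progression follow-up is planned, follows from the text without assumptions.

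The numbers are illustrations. Apparent hazard ratios of about 1.1 to 1.3 (36- to 120-month windows) and about 1.4 (360 months), against a true 1.5, rest on exponential times, a 30-month median and uniform ADT start. Attenuation is likely for short or moderate look-back, but it is not established. Power of roughly 10 to 20% rests on assumed hazard ratios of 1.5 to 1.76 and on every advanced-disease subject having an event. Low power is the more secure reason to expect an uninformative result.

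The importance is moderate. The comparison serves no listed objective and does not touch the primary analysis, but it would produce a p-value under secondary efficacy.

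**What to change.** In 7.3.2, remove the hypothesis test and replace the comparison with an exploratory, retrospective description:

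- Restrict it to advanced-disease subjects.
- Describe time from ADT start to failure by genotype, with failure defined.
- Label it as conditional on prior ADT failure, and list separately any man admitted under 2.1.1.4 without documented failure.
- Name the ADT start and failure dates among the history items in 3.6.1.1.

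If a test is kept, use a method for right-truncated data and state the look-back it assumes.

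The cost is wording and two history dates per advanced-disease subject. One analysis outside the objectives loses its p-value. Describing log signal change by genotype is an optional addition and not part of this correction. Separately, the 10 advanced-disease subjects in 3.1 and the 15 in the Precis and 7.1 need to be reconciled.

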#### **7.4 Sample Size Determination**

Sample size and power calculation is based on comparing signal change between pre- and post-injection in each subgroup separately. Based on a prior study on liver cancer patients, up to 3-fold mean signal change may be detected and the standard deviation of log-transformed signal ratio is approximately 0.25. With 10 evaluable patients in subgroup 2 (late stage), there is more than 95% power to detect a 2-fold mean signal change between pre- and post-injection at 5% significance level. For the first subgroup, OATP1B3 expression is likely lower and hence smaller signal change is expected. With 10 evaluable patients in each of these two subgroups, there is 83% power to detect a minimal 1.2 fold mean signal change. Higher power may be achieved if each patient has multiple lesions. Signal changes of multiple lesions from the sample patients will be averaged, and the comparison is based on the paired t-test using log-transformed signal values on a subject basis.

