## **7 STATISTICAL CONSIDERATIONS**

### **7.1 Study Populations**

25 evaluable patients will be included in this trial with an accrual rate of 1-2 patients a month. Therefore, it is expected that this study enrollment will be completed within 1.5 years and full study goals within 2.5 years. We plan to enroll 25 evaluable patients (10 in arm 1 and 15 in arm 2).

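### Section 7.4 bases its power on 10 patients per subgroup although the Precis and Section 7.1 plan 15 in arm 2, and its 83% depends on a log scale that is not stated

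*Combined protocol and SAP*

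**What the plan says.** Section 7.4 powers the pre- versus post-injection comparison separately in each subgroup. It takes the variability from an earlier liver cancer study: "the standard deviation of log-transformed signal ratio is approximately 0.25". The test is specified as follows: "the comparison is based on the paired t-test using log-transformed signal values on a subject basis".

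Two power statements follow, both for 10 patients:

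- Advanced disease: "With 10 evaluable patients in subgroup 2 (late stage), there is more than 95% power to detect a 2-fold mean signal change", at the 5% level.
- Smaller change, which the section expects in the localized subgroup: "With 10 evaluable patients in each of these two subgroups, there is 83% power to detect a minimal 1.2 fold mean signal change".

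Neither Section 7.3.1, which defines the primary analysis on log-transformed values, nor Section 7.4 names the base of the logarithm or says whether the test is one- or two-sided.

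On size, Section 7.1 plans "25 evaluable patients (10 in arm 1 and 15 in arm 2"), and the Precis agrees. Section 3.1 gives a total of 20 evaluable subjects, 10 in each disease group.

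**The concern.** A power figure should describe the trial that will be run and should be reproducible from the inputs printed beside it. The 83% fails on both counts.

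No power statement in Section 7.4 uses 15 patients, although two other places give that size for arm 2.

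The paired test gives the same p-value whatever log base is used in the analysis, but the planning SD does not carry over in that way. An SD of 0.25 in log2 units is 0.25 × ln 2 = 0.173 in natural-log units, so the base decides how much noise was assumed. The 1.2-fold statement is the one relevant to the localized arm, where the smaller change is expected and where all the sections agree on 10 patients. A reader who has to interpret a null result in that arm needs to know whether the planned chance of missing a true 1.2-fold change was about 16% or about 46%.

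**Working it through.** **Inputs**

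- SD of the log ratio: 0.25 (Section 7.4). It is the SD of the ratio, so it is already the SD of the paired difference.
- Effect: a 1.2-fold change (Section 7.4).
- n = 10 (Section 7.4, Section 3.1, and arm 1 everywhere); n = 15 (arm 2 in the Precis and Section 7.1).
- Level: 5% (Section 7.4). Two-sided is my assumption.

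**Formula.** Paired t-test power from the noncentral t distribution with n − 1 degrees of freedom:

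noncentrality = [log(1.2) / 0.25] × √n; power = P(|T| > critical t).

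The critical t is 2.262 for n = 10 and 2.145 for n = 15.

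**Reproducing the plan's figure (n = 10)**

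| Scale of the SD | log(1.2) | ÷ 0.25 | × √10 | Power |
|---|---|---|---|---|
| log2 | 0.2630 | 1.052 | 3.327 | 84.1% |
| natural log | 0.1823 | 0.729 | 2.306 | 53.9% |
| log10 | 0.0792 | 0.317 | 1.002 | 14.6% |

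Log2 is the only base near 83%. The one-point gap is within rounding: taking log2(1.2) as 0.26 gives 83.2%, and an SD of 0.254 gives 82.9%. Simulation (40,000 runs) gives 84.0% for log2 and 54.0% for natural log. The signed-rank alternative named in Section 7.3.1 gives 82.2% and 52.0%.

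**Can natural log reach 83% with the stated inputs?** Not with 10 patients. A one-sided t-test gives 68.6%, a two-sided normal approximation 63.5% and a one-sided normal approximation 74.6%. Reaching 83% means changing an input: n = 18, an SD of about 0.176, or a change of about 1.30-fold.

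**Does the other power statement settle the base?** For a 2-fold change with n = 10, power exceeds 99.9% on both log2 and natural log, and is 92.2% on log10. The claim of more than 95% therefore rules out log10 but does not separate the other two.

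**The 15-patient arm (1.2-fold, two-sided)**

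| Scale of the SD | × √15 | Power |
|---|---|---|
| log2 | 1.052 × 3.873 = 4.075 | 96.6% |
| natural log | 0.729 × 3.873 = 2.824 | 74.8% |
| log10 | 0.317 × 3.873 = 1.227 | 20.8% |

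None of these is 83%.

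**Arm sizes side by side**

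| Place | Localized | Advanced | Total |
|---|---|---|---|
| Precis | 10 | 15 | 25 |
| Section 3.1 | 10 | 10 | 20 |
| Section 7.1 | 10 | 15 | 25 |
| Section 7.4 (power) | 10 | 10 | not stated |

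**The case against.** The strongest reply is that the 83% is right. It comes out on log2 to within rounding, every effect in Section 7.4 is a fold change, for which log2 is a natural scale, and nothing in the documents says natural log. This stands. A reader might infer that the true power is 54% and that the sponsor miscalculated. The documents do not support that: natural log as the usual reading is only a convention, and adopting it means supposing an error as well. The figures that depend on it (54%, 18 patients, an SD of 0.176) are conditional.

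The second reply is that 15 patients give more power than 10 on any given scale, so a calculation for 10 is conservative for arm 2, and arm 1 is unaffected. This also stands as to direction. It does not make the statement describe a 15-patient arm, and it does not resolve Section 3.1.

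Third, a reader might go on to infer that a null result in the localized arm would be taken as absence of uptake. The documents do not say so. Section 1.2.4 says the agent quickly enhances all vascular tissue, which makes a null early comparison unlikely. Even on natural log, 10 patients have about 84% power at 1.3-fold. The study is also a pilot.

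What these replies leave open is that the scale can be recovered only by working backwards from the figure being checked. The earlier liver cancer study that supplies the SD is not identified in Section 7.4, so its scale cannot be looked up.

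**Conclusion.** The point holds as a mismatch of sample sizes and an undeclared scale, not as an arithmetic error.

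- **Sample size.** The power statements use 10 patients per subgroup. Under the Precis and Section 7.1, arm 2 has 15, and for that arm 83% is not the power on log2 (96.6%) or on natural log (74.8%). If log2 was used, the plan understates arm 2's power by about 14 points (96.6 − 83 = 13.6).
- **Scale.** For the 10-patient localized arm, the printed figure is sound on log2 (84.1%), the probable reading. It would be 53.9% on natural log, a gap of about 30 points that rests on one missing word.

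The figures assume a two-sided 5% paired t-test, normally distributed log ratios and 0.25 as the SD of the paired log difference. The 2-fold claim of more than 95% is safe on log2 or natural log at either arm size.

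**What to change.** 1. Reconcile the arm sizes in the Precis and Sections 3.1, 7.1 and 7.4, so that one pair of numbers appears throughout.
2. In Section 7.4, state the log base of the 0.25 SD and that the test is two-sided, if it is.
3. Restate the power for a 1.2-fold change at the final sizes:
   - if log2: about 84% with 10 patients and 97% with 15;
   - if natural log: 54% with 10 (about 83% only for a 1.30-fold change) and 75% with 15.

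If the base cannot be recovered from the source of the SD, print both sets and label the natural-log set as a conditional scenario.

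The cost is about two sentences in Section 7.4 and a corrected count wherever the sizes disagree. The test and the data collection stay as they are, and the restatement itself calls for no change in enrolment. The only exposure is that the localized-arm figure becomes less favourable if the SD proves to be on the natural-log scale.

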### **8 HUMAN SUBJECTS PROTECTION**

#### **8.1 Rationale for Subject Selection**

The patient population in whom this disease occurs is adult males. All ethnic groups/ race categories would be represented as they are represented in the disease as a whole. Cognitively impaired individuals will not be included in this study if they are unable to understand the informed consent. Physically impaired persons who otherwise satisfy eligibility criteria will be included in this study. This study is considered more than minimal risk to subjects and no direct benefits to the patient are expected. We anticipate that a thorough discussion of the study at the time informed consent is obtained will minimize any susceptibility to undue influences and unnecessary risks to research subjects.

#### **8.2 Participation of Children**

Prostate cancer is not seen in children. Thus, we will not include children in this study.

#### **8.3 Evaluation of Benefits and Risks/Discomforts**

There is no possibility of direct benefit to participants in this study. The results of this trial could generate generalizable information that may benefit future patients with prostate cancer and therefore, subjects may benefit by knowing they have contributed to scientific knowledge.

The risks for participating are also minimal. Because the risks of Eovist® injection and MRI are uncommon, we anticipate a low rate of adverse events at the FDA-approved, low-dose level used in this study.

#### **8.4 Risks/Benefits Analysis**

Specific risks and potential complications will be clearly outlined in a separate consent form at the time of each procedure. Most complications are expected to be minor and require no treatment. Risks and discomforts associated with Eovist® injection and imaging are discomfort of an IV placement and the theoretical effects allergic reaction. The subject will be required to lay still on their back for back for 5-7 minutes for the MRI scan. The scan will give valuable information about the OATP1B3 status of prostate tumors and could lead to Improvements in prostate cancer therapies targeted to OATP1B3. Adults who are or may be unable to consent are excluded.

#### **8.5 Consent and Assent Process and Documentation**

The subject will be informed of the study by a member of the study team. Written and oral information about the study in a language understandable by the subject will be given to all subjects. The study will be explained in detail and the consent form and protocol (if requested) will be provided to the subject to take home (if desired) for consideration. If the subject has any questions they will be answered at the time of initial protocol discussion or later by telephone. Each subject's willingness to participate in the study will be documented in a signed and dated informed consent form before any procedures or assessments are done and after the aims, methods, anticipated benefits, potential hazards, and insurance arrangements in force are explained. It will also be explained to the subjects that they are free to refuse entry into the study and free to withdraw from the study at any time without prejudice to future treatment. The informed consent process will be documented in the subject's medical record and the investigator will sign, and date the informed consent form after the subject and/or legal representative has signed and dated it. The investigator(s) will keep the original consent forms and copies will be given to the subjects. Informed consent may be obtained from the patient by the PI, an associate PI or any clinical designee credentialed to obtain informed consent for any procedure.

